- The treatment duration will be up to 52 weeks.

- The visit frequency will include visits at weeks 1, 5, 13, 26, 39, 52, and 56.

Treatment of interest

The treatment of interest is LTP001 [REDACTED] mg daily on top of allowed standard of care treatment for PAH. The dose of the allowed concomitant medication should remain stable during the trial.

Number of Participants:

The study population is comprised of male and female adults with PAH. A total of approximately 40 participants are planned to complete the parent study CLTP001A12201 and meet the study entry criteria for this open label extension study.

Key Inclusion criteria:

- Written informed consent must be obtained before any assessment is performed.
- Participant is currently completing the Novartis-sponsored study CLTP001A12201 in PAH and completed key efficacy and safety procedures up to the end of treatment of the parent study, without meeting discontinuation criteria in the parent study.
- Willingness and ability to comply with scheduled visits, treatment plans and any other study procedures.
- In the opinion of the Investigator the participant would benefit from LTP001 treatment.

Key Exclusion criteria:

- History of hypersensitivity to the study treatment.
- Required or planned transplant or heart/lung surgery.
- Acute or chronic impairment (other than dyspnea), which would limit the ability to comply with study requirements, including interference with physical activity or execution of study procedures such as 6MWT (e.g., angina pectoris, claudication, musculoskeletal disorder, need for walking aids).
- Permanent discontinuation of Novartis drug in the parent study due to toxicity or disease progression, non-compliance to study procedures, withdrawal of consent or any other reason.

Treatment Groups:

Active treatment: LTP001 administered as [REDACTED] mg once daily CCI [REDACTED] (CCI [REDACTED]). Investigational study treatment dose adjustments and/or interruptions are not permitted.

Data Monitoring/Other Committee:

Yes; the DMC instituted for the parent study will also receive data from this extension study (see [Section 10.1.4 Committees Structure](#)).

Key words:

Pulmonary arterial hypertension, pulmonary vascular resistance, 6 minute walk distance, time to clinical worsening, SMURF1 inhibitor, echocardiography, patient reported outcomes

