Period	Baseline		Extension Treatment Up To Month 12							
Visit Name	Transition Period		Treatment						EOT	Post Study Safety Contact
Visit Numbers ¹	1 ²	100 ²	110		120		130	140	150	
Days	-14 to -1	1	29 ±7	57 ±10	85 ±10	113 ±10	176 ±10	267 ±10	358 ±10	Last treatment +30 -0 +7
Weeks	-2 to -1	1	5 ±1	9 ±2	13 ±2	17 ±2	26 ±2	39 ±2	52 ±2	57 -0 +1
Informed consent ^{3,4}	X									
Inclusion / Exclusion criteria	X									
Physical Examination			S	S ⁸	S	S ⁸	S	S	S	
Body Weight			X	X ⁸	X	X ⁸	X	X	X	
Body Temperature			X	X ⁸	X	X ⁸	X	X	X	
Blood Pressure and Pulse Rate			X	X ⁸	X	X ⁸	X	X	X	
Electrocardiogram (ECG)			X	X ⁸	X	X ⁸	X	X	X	
Dose administration ⁵	X	X	X ⁸	X	X ⁸	X	X	X	X	
Drug dispensation	X	X		X			X	X		
Collect study medication/perform drug accountability ⁵			X	X ⁸	X	X ⁸	X	X	X	
Urinalysis			X	X ⁸	X	X ⁸	X	X	X	
Pregnancy and assessments of fertility			S	S ⁸	S	S ⁸	S	S	S	
Hematology			X	X ⁸	X	X ⁸	X	X	X	
Clinical Chemistry			X	X ⁸	X	X ⁸	X	X	X	

Period	Baseline		Extension Treatment Up To Month 12								
Visit Name	Transition Period		Treatment						EOT	Post Study Safety Contact	
Visit Numbers ¹	1 ²	100 ²	110		120		130	140	150		
Days	-14 to -1	1	29 ±7	57 ±10	85 ±10	113 ±10	176 ±10	267 ±10	358 ±10	Last treatment +30 -0 +7	
Weeks	-2 to -1	1	5 ±1	9 ±2	13 ±2	17 ±2	26 ±2	39 ±2	52 ±2	57 -0 +1	
Coagulation Panel			X	X ⁸	X	X ⁸	X	X	X		
NT-proBNP				X		X		X	X		
emPHasis-10 and PAH-SYMPACT ⁶			X ⁷		X ⁷		X ⁷	X ⁷	X ⁷		
Right Heart Catheterization ⁴							X				
6-Minute Walk Test ⁴							X		X		
Echocardiogram ⁴							X		X		
Concomitant Medications/Adverse Events								X			
Study completion information									X		

Period	Baseline		Extension Treatment Up To Month 12							
Visit Name	Transition Period		Treatment					EOT	Post Study Safety Contact	
Visit Numbers ¹	1 ²	100 ²	110		120		130	140	150	
Days	-14 to -1	1	29 ±7	57 ±10	85 ±10	113 ±10	176 ±10	267 ±10	358 ±10	Last treatment +30 -0 +7
Weeks	-2 to -1	1	5 ±1	9 ±2	13 ±2	17 ±2	26 ±2	39 ±2	52 ±2	57 -0 +1
Safety Follow up Call			S		S					S

^X Assessment to be recorded in the clinical database or received electronically from a vendor

^S Assessment to be recorded in the source documentation only

¹ Visit structure given for internal programming purpose only

² Baseline and Day 1 can be on the same day or within a 14-day transition period

³ CCI

⁴ Assessment must be performed onsite. All other assessments may be performed at an off-site location.

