4.7 End of study definition

The end of the study is defined as the date of the last visit of the last participant in the study.

Study completion is defined as when the last participant finishes their last study visit and any repeat assessments associated with this visit have been documented and followed-up appropriately by the Investigator.

5 Study population

The study population will be comprised of male and female participants with pulmonary arterial hypertension.

Approximately 40 participants are expected to complete parent study CLTP001A12201 and meet the study entry criteria for this open label extension study.

The investigator must ensure that all participants being considered for the study meet the following eligibility criteria. No additional criteria should be applied by the investigator in order that the study population will be representative of all eligible participants.

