6.2.3 Instruction for prescribing and taking study treatment

LTP001 should be taken daily at approximately the same time each day **CCI**. On clinic visit days, the participant should take LTP001 during the clinic visit when instructed by the study staff. 6MWT and RHC assessment should be executed at approximately the same time after drug administration each time (tolerance window +/- 1 hour).

CCI

If vomiting occurs during the course of treatment, participants should not take the study treatment LTP001 again before the next scheduled dose.

Participants should be instructed not to make up missed doses. A missed dose is defined as a case when the full dose is not taken within 12 hours after the approximate time of the usual daily dosing. That day's dose should be omitted and the participant should continue treatment with the next scheduled dose.

The first day the participant is seen by an off-site health professional during the visit window, or the first day of a visit to the clinical site should be the dose recorded in the Dosage Form eCRF.

Novartis will provide the site with a participant study card to hand over to all study participants, which will state that the participant is participating in a clinical study and is receiving an investigational product. This participant study card will also include the contact information of the Study Doctor/Investigative Site. Designated study staff will instruct study participants to present this card to a medical care provider if they have any medical issues during the course of the study.

All kits of study treatment assigned by the IRT will be recorded in the IRT system.

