- Drug interrupted/permanently discontinued

6. Its outcome

Conditions that were already present at the time of informed consent should be recorded in medical history of the participant.

Adverse events (including lab abnormalities that constitute AEs) should be described using a diagnosis whenever possible, rather than individual underlying signs and symptoms.

Adverse event monitoring should be continued for at least 30 days following the last dose of study treatment.

Once an adverse event is detected, it must be followed until its resolution or until it is judged to be not recovered/not resolved (e.g. continuing at the end of the study), and assessment must be made at each visit (or more frequently, if necessary) of any changes in severity, the suspected relationship to the interventions required to treat it, and the outcome.

Information about adverse drug reactions for the investigational drug can be found in the Investigator's Brochure (IB).

Abnormal laboratory values or test results constitute adverse events only if they fulfill at least one of the following criteria:

- they induce clinical signs or symptoms
- they are considered clinically significant
- they require therapy

Clinically significant abnormal laboratory values or test results must be identified through a review of values outside of normal ranges/clinically notable ranges, significant changes from baseline or the previous visit, or values which are considered to be non-typical in a participant with the underlying disease.

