8.6.3 SAE reporting

To ensure participant safety, every SAE, regardless of causality, occurring after the participant has provided informed consent and until 30 days following the last administration of study treatment must be reported to Novartis safety immediately, without undue delay, but under no circumstances later than within 24 hours of obtaining knowledge of the events (Note: If more stringent, local regulations regarding reporting timelines prevail). Detailed instructions regarding the submission process and requirements are to be found in the Investigator folder provided to each site. Information about all SAEs is collected and recorded on the Serious Adverse Event Report Form; all applicable sections of the form must be completed in order to provide a clinically thorough report.

1. SAEs occurring after the participant has provided informed consent until the time the participant is deemed a Screen Failure must be reported to Novartis.
2. Randomized OR Treated Participants: SAEs collected between time participant signs ICF until 30 days after the participant has discontinued from study treatment.

All follow-up information for the SAE including information on complications, progression of the initial SAE and recurrent episodes must be reported as follow-up to the original episode immediately, without undue delay, but under no circumstances later than within 24 hours of the Investigator receiving the follow-up information (Note: If more stringent, local regulations regarding reporting timelines prevail). An SAE occurring at a different time interval or otherwise considered completely unrelated to a previously reported one must be reported separately as a new event.

If the SAE is not previously documented in the Investigator's Brochure or Package Insert (new occurrence) and is thought to be related to the study treatment, a CMO & PS Department associate may urgently require further information from the Investigator for health authority reporting. Novartis may need to issue an Investigator Notification (IN) to inform all Investigators involved in any study with the same study treatment that this SAE has been reported.

Suspected Unexpected Serious Adverse Reactions (SUSARs) will be collected and reported to the competent authorities and relevant ethics committees in accordance with EU Guidance 2011/C 172/01 or as per national regulatory requirements in participating countries.

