The safety and efficacy of LTP001 will be checked at the following visits: Weeks 5, 13, 26, 39 and 52, as specified in the Assessment Schedule. Safety and tolerability assessments will take place at each visit. RHC will be performed at week 26 and 6MWT and echocardiography will be assessed at Weeks 26 and 52. PAH-SYMPACT and emPHasis-10 will be collected for 7 day intervals with the seventh day of collection occurring within the allotted visit window for all Treatment visits (Weeks 5, 13, 26, 39 and 52). Participants will have safety follow-up phone calls at Weeks 9 and 17, and may be invited for safety assessment at site if deemed necessary. The PI may exercise their discretion in which safety assessments are required at these optional safety follow-up visits. Following the end of treatment period, participants will have one safety follow-up phone call approximately 30 days after the end of treatment visit at Week 52. The duration of the extension study is currently restricted to 52 weeks, but the study may be prolonged (via an amendment to the protocol) if the LTP001 development program in PAH continues and the benefit/risk assessment remains favorable for the patient population studied. The safety and efficacy profile of LTP001 that is observed in this extension study as well as the parent study, CLTP001A12201, will determine continuation of the extension study.

Please refer to [Figure 1-1](#) for study design figure.

Figure 1-1 Study Schema

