2.1.1 General definitions

Investigational treatment will be LTP001.

Date of first administration of study treatment (Day 1) will be defined as the date of the first actual administration of LTP001.

Date of last administration of study treatment will be defined as the date of the last actual administration of LTP001.

Two *Baselines* will be defined as the following:

Baseline of the Parent study: the Day 1 assessment of study LTP001A12201. If this datum is not available, the last pre-dosing assessment will be considered.

Baseline of the Extension study: Week 25 visit from LTP001A12201. If this datum is not available, the last pre-dosing assessment for this study (LTP001A12201E1) will be considered. *Study day* will be defined as the number of days since the date of first dose of study treatment (LTP001 or placebo). The date of first dose of study treatment will be defined as *Day 1* and the day prior to first dose of will be defined as *Day -1*. Therefore, for a particular date, study day will be calculated as follows:

for dates on or after the date of first dose of study treatment,

Study day = Assessment date – Date of first dose administration + 1

The on-treatment period lasts from the date of first administration of study treatment to the End of Study (EOS) visit or the date of last randomized dose if EOS visit is not available. The EOS visit is a follow-up visit that is approximately 30 days after the date of the last actual administration of investigational treatment. For participants who will be enrolled into the open label extension (OLE) study, their EOS visits will be skipped.

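### The SAP's on-treatment period falls back to a dose that this extension does not have and, on the likeliest reading, labels deaths soon after the last dose by whether a later contact took place

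*SAP*

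**What the plan says.** SAP 2.1.1 starts the on-treatment period at the first administration of study treatment and ends it at the "End of Study (EOS) visit or the date of last randomized dose if EOS visit is not available". It describes EOS as a follow-up roughly 30 days after the last actual dose, and then says that participants going into the open-label extension skip it. The same section defines a date of last administration, based on the last actual LTP001 dose, but the fallback does not use it.

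SAP 1.1 calls the study non-randomized, and Protocol 6.3.1 marks randomization as not applicable.

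The protocol schedule has no visit named EOS. The only matching entry is the Post Study Safety Contact in Protocol Table 1-2, timed in the Days row as "Last treatment +30 -0 +7". SAP 1.1 describes the same call: "participants will have one safety follow-up phone call approximately 30 days after the end of treatment visit at Week 52".

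The protocol's collection windows do not depend on that call. Section 8.6.1 says "Adverse event monitoring should be continued for at least 30 days following the last dose of study treatment", and section 8.6.3 requires SAEs to be reported "until 30 days following the last administration of study treatment".

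SAP 2.5.1 points back to 2.1.1 for the on-treatment period. It promises a count and percentage of deaths, separated into on-treatment and post-treatment. Its laboratory shift tables use the worst on-treatment value, whereas SAP 5.3 takes worst values from all post-baseline results.

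**The concern.** Long-term safety is the primary objective, and the death split is one of its planned outputs. A reader takes an on-treatment death to be one close in time to dosing. Here the period has one length for participants who are reached afterwards and another for those who are not, and dying is itself a reason for not being reached. The outcome can therefore decide which length applies. The fallback also refers to a kind of dose that the extension does not give, so a programmer cannot apply it without guessing.

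**Working it through.** The plan states no figure to reproduce, and sample size is marked not applicable in Protocol 9.9 and SAP 3. The check applies the rule of SAP 2.1.1 to each calendar day after the last dose.

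**Literal reading.** The protocol describes the parent study as double-blind and refers to placebo, so its doses are presumably the randomized ones (an inference). The skipped-EOS sentence then puts every extension participant on the fallback, and the period ends at a parent-study dose. For former placebo participants that is before their first LTP001 dose, so no valid period exists. For former LTP001 participants it is before the extension begins. This cannot be the intention.

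**Workable reading.** Two assumptions are needed: EOS is the Post Study Safety Contact, and the fallback is the last extension LTP001 dose. A contact counts as not available if death comes first.

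Inputs:
- Planned end of treatment: Day 358 (Protocol Table 1-2).
- Contact: 30 to 37 days after last treatment (Table 1-2, Days row).
- Denominator: "Approximately 40 participants are expected to complete parent study CLTP001A12201" (Protocol 5), taken as 40 treated.

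End of the period for a last dose on Day 358:
- with the contact: 358 + 30 = Day 388, to 358 + 37 = Day 395;
- without it: Day 358, which is 0 post-dose days.

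Post-dose days labelled on-treatment, among the days before the contact:

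| Contact at | Death, as written | Non-fatal event, participant later reached, as written | Death, last dose + 30 days |
|---|---|---|---|
| +30 (days 1 to 29) | 0 of 29 | 29 of 29 | 29 of 29 |
| +37 (days 1 to 36) | 0 of 36 | 36 of 36 | 30 of 36 |

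Days 1 to 29 are affected wherever the contact falls in the Days-row window. A death on the calendar date of the last dose is still on-treatment. Protocol 6.2.3 says "LTP001 should be taken daily at approximately the same time each day", so post-dose day 1 includes a participant who never stopped treatment and dies on the day after a dose, before taking the next one.

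Size: one death is 1/40 = 2.5 percentage points, and two are 2/40 = 5.0 points, moved from the on-treatment to the post-treatment row.

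The contact date is itself stated inconsistently. With day = 7 × (week − 1) + 1, Week 52 is Day 358. The Weeks row (57, up to +1 week) gives Day 393 to Day 400, or 35 to 42 days after Day 358. Protocol 1.1 says "The visit frequency will include visits at weeks 1, 5, 13, 26, 39, 52, and 56", and Week 56 is Day 386, or 28 days after. This is a separate scheduling matter. It shifts the upper limit of the affected days but not the mechanism.

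**The case against.** The strongest reply is that the mechanism rests on readings that the SAP does not fix. EOS is never equated with the Post Study Safety Contact, and that call is marked for source documentation only in Table 1-2, so even a completed call may leave no EOS date in the database. The SAP does not define when EOS is not available. For participants who stop treatment and cannot attend visits, Protocol 7.1 allows telephone contact with a pre-designated person, and the SAP does not say whether that, or a death date entered as study end, counts as EOS. All of this stands. It means that the outcome-dependent label is the likeliest reading rather than a certain one. It does not rescue the definition, because no passage supplies a rule for death before the contact and the reference to a randomized dose is wrong on any reading.

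Three stronger inferences are tempting, and the documents do not support them.

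- A reader might infer that the on-treatment death row is empty by construction, or try to put a percentage on the misplaced deaths among participants still dosing. A death on a dosing date stays on-treatment, the availability of EOS is undefined, and the documents give neither dosing hours nor a death rate.
- A reader might infer that post-dose laboratory values are lost from the shift tables. SAP 2.5.1 speaks of on-treatment values but SAP 5.3 uses post-baseline values with no such cutoff, so no laboratory effect is established. The two passages need reconciling.
- A reader might infer that adverse events drop out. SAP 2.5.1 defines treatment-emergent events by their start or worsening relative to first dose, and does not say that the period truncates those tables.

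It is also fair to say that the stakes are small: the tables are descriptive, and every death is still counted and listed.

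**Conclusion.** The point holds in limited form, and the definition should be corrected. It is certain that the fallback names no dose in this extension and that the skipped-EOS sentence does not fit the extension. If EOS is the Post Study Safety Contact, the fallback is the last extension dose, and a participant who dies first has no contact, then a death on post-dose days 1 to 29 is labelled by the absence of a contact, not by time since last dose. The consequence is confined to the on-/post-treatment death split, at 2.5 percentage points per affected death with 40 treated. How many deaths would be affected cannot be estimated from the documents.

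**What to change.** For all extension outputs, define the on-treatment period in SAP 2.1.1 as running from the first extension LTP001 dose to the last actual extension LTP001 dose plus 30 days, or to death if earlier, whether or not the follow-up contact took place. Delete the reference to a randomized dose and the skipped-EOS sentence from the extension definition. Use one window for the worst laboratory value in SAP 2.5.1 and SAP 5.3.

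This matches the protocol's 30-day AE and SAE windows and no longer depends on which contact date is right. It costs SAP wording and one derived date, based on a last-dose date that the SAP already defines, with no new data. There are three downsides: participants lost or withdrawn contribute some unobserved days, events on post-dose days 31 to 37 fall outside the period, and the on-treatment death row may look less favourable.

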2.2 Analysis sets

For all analysis sets, participants will be analyzed according to the study treatment(s) received. The safety analysis set will include all participants that received any study treatment.

The PD analysis set will include all participants who received study treatment and had no protocol deviations with relevant impact on PD data.

The analysis sets and protocol deviation codes are related as [Table 2-1](#).

Table 2-1 Protocol deviation codes and analysis sets

Category Deviation code	Text description of deviation	Data exclusion
Subjects are excluded from Safety analysis in case of these PDs:		Exclude subject from Safety analysis set
INCL01	Subject withdrew consent but continue to receive study medication	Y
Subjects are excluded from PD analysis in case of these PDs:		Exclude subject from PD analysis sets
INCL01	Subject withdrew consent but continued to receive study medication	Y

Protocol deviations mentioned above, and analysis sets will be reviewed in the data review meeting to decide inclusion or exclusion of participant(s) from analyses sets. Decisions regarding the exclusion of participants and/or participant data from analyses will be made prior to final database lock (DBL).

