7.3 Withdrawal of informed consent and exercise of participants' data privacy rights

Withdrawal of consent/opposition to use of data and/or biological samples occurs in countries where the legal justification to collect and process the data is consent and when a participant:

- Explicitly requests to stop use of their data
and
- No longer wishes to receive study treatment
and
- Does not want any further visits or assessments (including further study-related contacts)

This request should be as per local regulations (e.g. in writing) and recorded in the source documentation.

Withdrawal of consent impacts the ability to further contact the participant, collect follow-up data (e.g. to respond to data queries) and potentially other country-specific restrictions. It is therefore very important to ensure accurate recording of withdrawal vs. discontinuation based on the protocol definitions of these terms.

In this situation, the Investigator should make a reasonable effort (e.g. telephone, e-mail, letter) to understand the primary reason for the participant's decision to withdraw their consent/exercise data privacy rights and record this information. The Investigator shall clearly document if the participant has withdrawn his/her consent for the use of data in addition to a study discontinuation.

Study treatment must be discontinued and no further assessments conducted, and the data that would have been collected at subsequent visits will be considered missing.

Further attempts to contact the participant are not allowed unless safety findings require communicating or follow-up.

If the participant agrees, a final evaluation at the time of the participant's withdrawal of consent/exercise data privacy rights should be made as detailed in [Section 1.3](#).

Further details on withdrawal of consent or the exercise of participants' data privacy rights are included in the corresponding informed consent form.

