2.5.2 Statistical hypothesis, model, and method of analysis

The long-term safety of LTP001 will be evaluated in this extension study.

All analyses will be based on frequency counts and summary statistics. No statistical models will be used.

The primary analysis population will be the Safety analysis set.

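### SAP Table 2-1 removes a dosed participant from the Safety set for one consent deviation, against the all-treated definition in SAP 2.2 and Protocol 9.1

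*SAP*

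**What the plan says.** SAP 2.2 defines the set without exception: "The safety analysis set will include all participants that received any study treatment". Protocol 9.1 uses the same sentence. In both documents the definition of the PD set that follows does carve out protocol deviations. The Safety definition does not.

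Table 2-1, also in SAP 2.2, then introduces a Safety-set exclusion ("Subjects are excluded from Safety analysis in case of these PDs"), with the instruction "Exclude subject from Safety analysis set" marked Y for one code, INCL01: "Subject withdrew consent but continue to receive study medication". SAP 5.5 points back to this table as the rule for exclusions.

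The text under the table says that the listed deviations and analysis sets "will be reviewed in the data review meeting to decide inclusion or exclusion of participant(s) from analyses sets". It allows decisions about participants or about participant data, to be made before database lock.

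SAP 2.5.2 states: "The primary analysis population will be the Safety analysis set". SAP section 4, on changes to protocol-specified analyses, reads as not applicable.

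On withdrawal of consent, Protocol 7.3 requires study treatment to stop and adds that "the data that would have been collected at subsequent visits will be considered missing". The same section and the glossary in 10.2.2 define withdrawal as including an explicit request to stop use of the participant's data.

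**The concern.** A safety population normally has one entry condition, exposure to the drug, so that nobody who could have had an adverse reaction is left out of the count. Here a second rule removes a participant who is exposed by definition, and removes the person rather than the affected records. Everything recorded on that participant would leave the AE, SAE, laboratory, ECG and vital-sign summaries, including whatever was collected before consent was withdrawn.

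This matters because safety is the primary objective and the set is small, at about 40 participants. Losing one person hardly changes the rate of a common event, but can delete the only occurrence of a rare one. A reader of the report who sees the set described as all treated would not know this without going to the exclusion listing.

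**Working it through.** **Step 1: the two rules side by side.**

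- Definition (SAP 2.2, Protocol 9.1): received any study treatment, therefore in.
- Table 2-1: withdrew consent and went on receiving study medication, therefore out.

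Anyone meeting the second condition also meets the first. The two rules give opposite answers for every INCL01 participant. The protocol has no such exclusion and SAP section 4 reports no change, so the departure is undeclared.

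**Step 2: what the exclusion follows.** Take two participants who withdraw consent on the same day.

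| | Stops dosing | Continues dosing |
|---|---|---|
| Consent withdrawn | yes | yes |
| Listed in Table 2-1 | no | yes (INCL01) |
| Safety set under Table 2-1 | in | out |

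If the reason were the right to have data no longer used, both would be treated alike. The only difference is continued dosing, so the rule removes the participant with the longer exposure.

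**Step 3: size.** The plan has no figure to reproduce: sample size is not applicable (Protocol 9.9, SAP 3), and the primary analysis is counts and summary statistics. What follows is illustration only. The inputs are 40 treated participants (the approximate number in Protocol 1.1 and section 5) and an assumed number of INCL01 participants, since the documents give none. The intervals are exact (Clopper-Pearson) 95% intervals for x events in n: the lower limit is the 2.5% quantile of Beta(x, n−x+1), and the upper limit is the 97.5% quantile of Beta(x+1, n−x). For x = 0 the lower limit is 0 and the upper limit is 1 − 0.025^(1/n), which for n = 39 is 9.0%.

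| Assumed case | All treated kept | INCL01 excluded |
|---|---|---|
| One INCL01, who has the only event | 1/40 = 2.5% (0.06% to 13.2%) | 0/39 = 0% (0% to 9.0%) |
| One INCL01, who has one of two events | 2/40 = 5.0% (0.6% to 16.9%) | 1/39 = 2.6% (0.06% to 13.5%) |
| One INCL01 without the event, four others with it | 4/40 = 10.0% | 4/39 = 10.3% |
| Three INCL01, who have all three events | 3/40 = 7.5% (1.6% to 20.4%) | 0/37 = 0% (0% to 9.5%) |

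The loss of sample size itself is negligible. For an event with a true rate of 2.5%, the chance of seeing at least one case is 1 − 0.975^40 = 63.7% with 40 participants and 1 − 0.975^39 = 62.7% with 39. What matters is which participant is lost.

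**The case against.** The strongest defence is privacy. INCL01 begins with withdrawal of consent, and Protocol 7.3 and the glossary define that as including a request to stop use of data. A participant who merely discontinues has a separate status without such a request. On this view the exclusion respects the participant's wishes.

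Part of this stands. A reader might infer that the data collected before withdrawal are consented and free to use, because Protocol 7.3 calls only later data missing. The documents do not support that. The sentence is silent on earlier data, the definition includes a request to stop use, and further detail is left to the consent form, which is not available here. An exemption limited to legally required erasure would therefore be too narrow.

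The defence does not explain the rule as written, however, because withdrawal without further dosing triggers no listed exclusion. Nor can a data-use request be assumed for everyone coded INCL01: the protocol's definition also requires that the participant no longer wants treatment, which fits poorly with continuing to take it.

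The second defence is that exclusion is not automatic. The data review meeting decides, may act at record level, and does so before database lock. SAP 2.3.1 already plans a listing of excluded participants with reasons. This softens the problem. It still leaves two conflicting written rules to be settled case by case in an open-label study, and a listing does not put events back into the summaries.

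Two stronger readings should be set aside. One is that the rule always biases event rates downward. It does so only if the excluded participant had the event; otherwise the rate rises slightly, as in 4/40 to 4/39. The other is that it could hide a death before withdrawal. That cannot happen, since the participant must be alive to withdraw and to continue dosing.

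**Conclusion.** The contradiction is real and lies in the definition of the primary analysis population. Table 2-1 orders subject-level exclusion of people whom SAP 2.2 and Protocol 9.1 include, and the change is not declared.

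The expected numerical effect is small. Protocol 7.3 requires treatment to stop at withdrawal, so INCL01 cases should be rare, and common-event rates would barely move. The exposure is to selective loss of a rare event: in the illustration, 2.5% with an upper limit of 13.2% becomes 0% with an upper limit of 9.0%. This assumes 40 treated participants, one INCL01 case who is also the only case of the event, and a meeting that applies the table as written. The intervals are not planned outputs; they only show the scale.

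Whether data from before withdrawal may be used is not settled by the documents, and this conclusion does not depend on it. The point should be corrected before database lock.

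**What to change.** Replace the Safety-set row of Table 2-1 with a rule that matches the definition:

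- Every treated participant stays in the Safety set.
- Only records whose use is barred by the withdrawal request, the consent form or local law are dropped; at minimum, those after the withdrawal date.
- The same rule applies whether or not dosing continued after withdrawal.
- The report gives the number of INCL01 cases, with whatever exposure and SAEs may lawfully be reported.

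If subject-level exclusion is truly intended, amend the Safety set definition to say so, and declare and justify the change in SAP section 4.

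The cost is one table row and a few sentences in the SAP, plus a check of the consent form and local law for each case that arises. No new data are needed. Some data from before withdrawal may still prove unusable, and the rule above allows for that.
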